5.3.4. Physical Activity

- Participants will abstain from strenuous exercise for 24 hours before each blood collection for clinical laboratory tests. Participants should maintain stable levels of physical activity throughout the duration of screening, treatment and follow up.
- Participants may continue a regimen of therapeutic exercise, provided it has been stable for at least 4 weeks prior to enrolment. No new therapeutic regiments should be implemented during the study. Physical therapy or therapeutic massage should not be initiated during this study
- Heat or ice therapy can be used during the study, except 2 hours prior to eDiary assessments and 24 hours prior to a clinic visit

5.4. Screen Failures

Screen failures are defined as participants who consent to participate in the clinical study but are not subsequently randomized. A minimal set of screen failure information is required to ensure transparent reporting of screen failure participants to meet the Consolidated Standards of Reporting Trials (CONSORT) publishing requirements and to respond to queries from regulatory authorities. Minimal information includes demography, screen failure details, eligibility criteria, and any SAEs.

5.4.1. Re-screening

Individuals who do not meet the criteria for participation in this study (screen failure) may be rescreened once. Individuals who screen fail due to running out of time in the screening window due to non-medical reasons e.g. for a short notice covid booster vaccine may be rescreened more than once following discussion with the medical monitor. Rescreened participants should be assigned a new participant number. Participants who have tested positive for COVID-19 will not be re-screened.

5.4.2. Re-testing of Clinical Laboratory Values during Screening

If a participant fails any of the laboratory criteria, the test may be repeated once within the screening period. If the participant fails, the laboratory criteria for a second time they will be considered a screen failure.

If a blood sample needs to be repeated due to sample handling problems, breakage or sample integrity, this is not considered a re-testing. Further details regarding the procedure for re-testing may be found in the Study Reference Manual (SRM).

6. STUDY INTERVENTION

Study intervention is defined as any investigational intervention(s), marketed product(s), placebo, or medical device(s) intended to be administered to a study participant according to the study protocol.

6.1. Study Intervention(s) Administered

Study intervention is defined as any product received by the participant as per the study protocol. Study intervention may therefore refer to GSK3858279 or placebo.

Table 3 Study interventions

Product name:	GSK3858279	Diluent/Placebo
Formulation description:	GSK3858279 is formulated in 0.79 mg/mL sodium acetate, 50 mg/mL sorbitol, 0.4 mg/mL polysorbate 20, glacial acetic acid 0.28 mg/mL, water for injection, pH 5.0. GSK3858279 contains no preservative.	Normal Saline (0.9% sodium chloride)
Dosage form:	Solution for injection	Solution for injection
Unit dose level:	50 mg/mL. Each vial has an extractable volume of 3.0 mL (150 mg per vial).	0.9% w/v sodium chloride, placebo level variable.
Route of administration and duration:	IV or SC	IV or SC
Dosing instructions:	IV cohorts 1-5: GSK3858279 will be infused over up to 1 hour. GSK3858279 can be diluted in normal saline prior to administration. SC Cohorts 6 (Part A) ¹ and 7 (Part B) ² The appropriate volume of GSK3858279 will be injected using a syringe at	The appropriate volume of normal saline will be infused (IV) or injected (SC) in the same manner as the corresponding active cohort.

	no more than 1.2 mL per injection.	
Physical description:	The drug product is a brown to yellow solution stored in 5 mL glass vials with a 20 mm rubber stopper and a grey-brown 20 mm Flip-top aluminium overseal.	Commercial presentation
Manufacturer/source of procurement:	Study medication is supplied by GSK.	0.9% w/v sodium chloride is sourced locally by the site.

¹⁾ Part A: As a maximum of 4 SC injections will be administered for feasibility reasons, the maximum dose that will be administered to participants weighing >80 kg will be 240 mg.
2) For Part B, all participants are to receive a weekly dose of 240 mg SC (4 x 1.2 mL injections) irrespective of weight.

The doses of GSK3858279 for injection will be prepared at the clinical site by an unblinded pharmacist from the stock solution provided (see Table 3).

6.2. Preparation/Handling/Storage/Accountability

• The investigator or designee must confirm appropriate temperature conditions have been maintained during transit for all study intervention received and any discrepancies are reported and resolved before use of the study intervention.

Only participants enrolled in the study may receive study intervention and only authorized site staff may supply or administer study intervention. All study interventions must be stored in a secure, environmentally controlled, and monitored (manual or automated) area in accordance with the labeled storage conditions with access limited to the investigator and authorized site staff.

The investigator, institution, or the head of the medical institution (where applicable) is responsible for study intervention accountability, reconciliation, and record maintenance (ie, receipt, reconciliation, and final disposition records).

Further guidance and information for the final disposition of unused study intervention are provided in the SRM.

- Under normal conditions of handling and administration, study intervention is not expected to pose significant safety risks to site staff. Take adequate precautions to avoid direct eye or skin contact and the generation of aerosols or mists. In the case of unintentional occupational exposure notify the monitor, Medical Monitor and/or GSK study contact.
- A Material Safety Data Sheet (MSDS)/equivalent document describing occupational hazards and recommended handling precautions either will be provided to the investigator, where this is required by local laws, or is available upon request from GSK.

6.3. Measures to Minimize Bias: Randomization and Blinding

6.3.1. Randomization

At Screening a unique Participant Number (case report form [CRF] number) will be assigned to any participant who has at least one Screening procedure performed, other than informed consent. The unique Participant Number will be used to identify individual participants during the course of the study.

Participants who meet the screening eligibility criteria will be randomised to a treatment group through RAMOS NG. The randomisation is centrally controlled by RAMOS NG. RAMOS NG will confirm the participants CRF number (Participant number) and provide the randomisation number, where:

• A randomisation number will be assigned from a randomisation schedule generated by Clinical Statistics, prior to the start of the study, using validated internal software. Once assigned, this number must not be reassigned to any other participant in the study.

Part A

Within each cohort, participants will be assigned to either GSK3858279 or placebo in a 3:1 ratio, where the intervention codes are as follows:

Intervention code	Intervention Description
A	0.1 mg/kg IV GSK3858279
В	0.3 mg/kg IV GSK3858279
С	1 mg/kg IV GSK3858279
D	3 mg/kg IV GSK3858279
Е	10 mg/kg IV GSK3858279
F	SC GSK3858279
P	Placebo

Part B

Participants will be assigned to either GSK3858279 or placebo; where the GSK3858279 dose level to be studied in Part B will be dependent on the Part A data. The randomisation ratio will be 1:1 for GSK3858279: placebo.

Intervention code	Intervention Description
G	240 mg SC GSK3858279
P	Placebo

6.3.2. Blinding

This will be a double-blind study with respect to allocation of GSK3858279 or placebo to participants and the following will apply.

- The investigator or treating physician may unblind a participant's intervention assignment **only in the case of an emergency** OR in the event of a serious medical condition when knowledge of the study intervention is essential for the appropriate clinical management or welfare of the participant as judged by the investigator.
- The interactive voice response system (IVRS)/ interactive web recognition system (IWRS) will be programmed with blind-breaking instructions. In case of an emergency, the investigator has the sole responsibility for determining if unblinding of a participant's intervention assignment is warranted. Participant safety must always be the first consideration in making such a determination. If the investigator decides that unblinding is warranted, the investigator should make every effort to contact GSK prior to unblinding a participant's intervention assignment unless this could delay emergency treatment of the participant. If a participant's intervention assignment is unblinded GSK must be notified within 24 hours after breaking the blind. The date and reason that the blind was broken must be recorded in the source documentation and CRF, as applicable.
- If GSK personnel are not contacted before the unblinding, the investigator must notify GSK as soon as possible after unblinding, but without revealing the intervention assignment of the unblinded participant, unless that information is important for the safety of participants currently in the study.
- The date and reason for the unblinding must be fully documented in the CRF
- A participant will be withdrawn if the participant's intervention code is unblinded by the investigator or treating physician. The primary reason for discontinuation (the event or condition which led to the unblinding) will be recorded in the CRF. The participant will be followed up for safety monitoring if treatment was received.
- GSK's SMG staff may unblind the intervention assignment for any participant with an SAE. If the SAE requires that an expedited regulatory report be sent to one or more regulatory agencies, a copy of the report, identifying the participant's intervention assignment, may be sent to investigators in accordance with local regulations and/or GSK policy.
- GSK DEC members may review unblinded safety data from Part A on an as required basis and at the dose escalation meetings, where no-one outside of this committee will be unblinded to the study data. Further details of how this will be managed are included in the DEP.
- Members of the study Interim Data Review Committee (IDRC) and senior GSK leadership may also review unblinded data from Part B at Interim Analyses as described in Section 9.4.5.
- There will be an unblinded site pharmacist to prepare the study intervention; however, they will not have contact with study participants.

6.4. Study Intervention Compliance

- When the individual dose for a participant is prepared from a bulk supply, the preparation of the dose will be confirmed by a second member of the study site staff.
- Participants will receive study intervention at the clinical unit directly from the investigator or designee, under medical supervision, via IV or SC route depending on the cohort the participant is enrolled into. The date and time of each dose administered in the clinic will be recorded in the source documents. The dose of study intervention and study participant identification will be confirmed at the time of dosing by a member of the study site staff other than the person administering the study intervention.

6.5. Concomitant Therapy

Any medication or vaccine (including over-the-counter or prescription medicines, vitamins, and/or herbal supplements) that the participant receives during the study must be recorded along with:

- reason for use
- dates of administration including start and end dates
- dosage information including dose and frequency

The Medical Monitor should be contacted if there are any questions regarding concomitant or prior therapy.

Participants will be provided with a diary card to record usage of any medications between visits

6.5.1. Permitted Therapies

In Part A, participants must abstain from taking prescription or non-prescription drugs (including vitamins and dietary or herbal supplements) within 7 days (or 14 days if the drug is a potential enzyme inducer) or 5 half-lives (whichever is longer) before the start of study intervention until completion of the follow-up visit, unless, in the opinion of the investigator and sponsor, the medication will not interfere with the study.

In Part B, the following medications are permitted if they were used at a stable dose for at least 30 days prior to screening:

- Antidepressant medication including selective Serotonin reuptake inhibitors (SSRI) and Serotonin Noradrenaline reuptake inhibitors (SNRI)
- Nutraceuticals (eg Glucosamine or Chondroitin)
- Aspirin for cardiovascular indications at a maximum dose of 300 mg/day

6.5.2. Rescue Medication (Part B)

In Part B, Paracetamol/Acetaminophen, at doses of ≤ 3 grams/day, is permitted for use as rescue medication any time during the study except 24 h before a clinical visit. The study site will supply rescue medication.

6.6. Prohibited Medications

The following are prohibited from Day -7 until Day 71. A washout period is required prior to Day -7, consisting of 3 days or 5 half-lives, whichever is longer. Refer to Figure 5.

- All pain medications including anti-neuropathic agents (e.g. Gabapentin and Pregabalin), opioids, NSAIDs, topical analgesics
- Adjunctive therapies

The following are prohibited throughout the entire duration of the study:

- Attenuated live vaccine(s)
- Biologic agents (monoclonal antibodies, therapeutic proteins)
- Antiplatelet or anticoagulant agents
- Immunosuppressants
- Systemic Corticosteroids
- Intra-articular therapy of the index joint

6.7. Dose Modification

Part A: The decision to proceed to the next dose level of GSK3858279 will be made by the DEC. The dose escalation decision will be based on safety, tolerability and preliminary PK data obtained in all participants at that dose level (through 15 days post dose). The actual doses to be administered may be adjusted based on safety, tolerability and preliminary PK data at previous dose levels; these dose adjustments may involve either an increase or a decrease in the planned dose, but will not exceed PK criteria (See Section 4.4 and Section 7.2.3), and the maximum dose administered in this study will not exceed the maximum planned dose of 10 mg/kg. Planned dose levels may also be repeated.

The Principal Investigator and the GSK Medical Monitor will review the following and dosing **will be** halted and progression to the next higher dose level stopped if:

- One (1) or more participants experience a serious adverse event which has a reasonable possibility of being causally related to study drug.
- Two (2) or more participants experience a severe or clinically significant non-serious adverse event (based upon investigator judgment) which has a reasonable possibility of relation to study drug. Three (3) or more participants in a cohort experience the same adverse event of moderate severity which has a reasonable possibility of relation to study drug.

Part B: Please see Dose Adjustment Pharmacokinetic Criteria (Section 7.2.3).

6.8. Intervention after the End of the Study

GSK will not provide treatment after the end of the study.

7. DISCONTINUATION OF STUDY INTERVENTION AND PARTICIPANT DISCONTINUATION/WITHDRAWAL

7.1. Study stopping criteria

Recruitment will be halted by the sponsor if any of the following occur in participants receiving GSK3858279:

Part A

- One participant experiences an SAE that is considered to be related to GSK3858279
- One participant experiences a significant clinical or laboratory abnormality that may plausibly relate to GSK3858279 (according to the clinical judgement of the investigator)
- Two participants present with unexpected and clinically significant mucocutaneous bleeding (according to the clinical judgement of the investigator).

Recruitment may be resumed after appropriate positive review of safety findings by the Principal Investigator, Medical Monitor and DEC, and following approval to restart the study from the regulatory agencies and ethics committees.

Part B

- Two participants experience a SAE that is considered related to GSK3858279. Please also refer to the next Section 8.5 (Adverse Events), Appendix 3 (Adverse Events) and the study-specific Safety Management Plan.
- Two participants experience the same significant clinical or significant laboratory abnormality that may plausibly relate to GSK3858279 (according to the clinical judgement of the investigator)
- Two participants present with unexplained and clinically significant mucocutaneous bleeding (according to the clinical judgement of the investigator and medical monitor) that is considered causally related to GSK3858279.

Recruitment may be resumed after appropriate positive review of safety findings by the Principal Investigators, Medical Monitor and SRT, and following approval to restart the study from the regulatory agencies and ethics committees.

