10.10.2. Amendment 2 21-NOV-2018

Overall Rationale for the Amendment: To address the points raised by both the Paul-Ehrlich-Institute (P-E-I letter dated 28-SEP-20018) and the UK Central Ethics Committee (letter dated 12-SEP-2018): principally to clarify the conduct of safety management. Incorporation of non-substantial changes (previously captured in File Notes (details below).

Section # and	Description of Change	Brief Rationale
Name		
Section 8.5 Adverse Events and Appendix 3	Reference to the study specific Safety Management Plan (SMP) has been included.	PEI's request to define, within the body of the protocol, the processes for prompt communication of SAEs/SUSARs and rapid implementation of corrective and preventive actions between Sponsor, all study sites and investigators.
Table 1.3.1 Schedule of Assessments (Screening)	Addition of Tb-Screening (QuantiFERON test) and FSH and estradiol (in women of non-childbearing potential).	PEI's request to include the screening assessments in the Schedule of Assessments.
Section 7.1 Study stopping criteria	Removal of duplication of "serious." Second bullet modified: "One patient experiences a "significant" clinical or laboratory abnormality.	CCI
		Recruitment will be halted by the sponsor (and may be resumed after appropriate positive review of safety findings and following approval from the regulatory agencies and ethics committees to restart. If deemed appropriate the Informed Consent may be revised.
3 and Figure 4	Weekly (7-day) visit arrangement corrected from Days 112 and 140 to Days 113 and 141, respectively.	Corrected to ensure consistency in scheduling, data collection, analysis and reporting (File Note 4-OCT- 2018).
Section 4.1 and Figure 1	Removal of the interdependency of executing Cohort 7 (single intravenous dose in osteoarthritis patients, Part B) immediately following Cohort 6 (single subcutaneous dose in healthy subjects, Part A).	It is logical to execute Cohort 7 (single intravenous dose in osteoarthritis patients, Part B) following the review of the safety and tolerability of a single intravenous dose administered to healthy subjects in Cohort 5 (Part A).

Section # and Name	Description of Change	Brief Rationale

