10.10.3. Amendment 3 18-JUL-2019

Overall Rationale for the Amendment: To adjust the design of Part B from a single intravenous dose to repeat weekly subcutaneous injections over a period of 8 weeks to provide adequate exposure to test the effect on pain in participants with OA of the knee.

Areas of the protocol impacted are: Dose regimen; Treatment Period; Follow-Up Period; Safety Review; Safety Mitigation and Monitoring; Participant Numbers and Interim Analysis; Individual Participant and Study Stopping Rules.

Other areas adjusted are: Patient Population; Patient Global Assessment of Disease Activity, Rescue and Prohibited Medications; PainDETECT; Participant Feedback Questionnaire.

Minor changes and corrections are made throughout to provide refinement and clarification.

MAIN Section # and Name	Description of Change	Brief Rationale
Section 4.4 Justification for Dose	Dose regimen: from a single intravenous dose (two dose levels) to repeat weekly subcutaneous injection of 240 mg (4 injections).	During dose escalation of Part A, a review of pharmacokinetic (PK) and target engagement (TE) data, indicated a much faster clearance of GSK3858279 than was originally predicted. Repeat weekly subcutaneous (SC) dosing is required to provide adequate exposure to test the potential to effect pain in participants with OA of the knee.
Section 3 Objectives and Endpoints	Adjusted the primary objective of Part B for assessment of efficacy following repeat dosing Included rescue medication as	Both safety and efficacy are evaluated. Rescue medication is a
	a component of the efficacy endpoint.	component of the efficacy endpoint.
Section 4.1.1 Treatment Groups and Duration	Treatment Period: from a single dose to 8 weeks of treatment	The secondary objective/endpoint (change from baseline in average weekly Daily Pain NRS) was set at 8 weeks to provide confidence of a clinically meaningful treatment effect vs placebo. Two additional visits (Day 36 and Day 50) are introduced into the schedule (dosing days). Day 2 is replaced by Day 4 to optimize pharmacokinetic sampling.
Section 4.1.1 Treatment Groups and Duration	CCI	

Protocol Am		
MAIN Section # and Name	Description of Change	Brief Rationale
	CCI	

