10.10.4. Amendment 4 14-NOV-2019

Overall Rationale for the Amendment 4 (for Part B): To address the concerns from the Ethics Committees' review of Amendment 3 (Part B).

Section # and Name	Description of Change	Brief Rationale
Section 3: Objectives and Endpoints	Corrected the row structure of the table	To properly reflect our intent to evaluate both safety and efficacy as the primary objectives for Part B.
Section 5.1 Inclusion Criteria	Reduce the upper limit of BMI from 39.9 kg/m ² to 34.9 kg/m ²	To exclude participants of > Grade 1 Obesity (and so to reduce the risk.
Section 5.2 Exclusion Criteria (No. 57, 60, 62 and 69)	No. 57: To also exclude participants with a history of primary cardiomyopathy No. 60: To clarify that participants who have a history of excessive bleeding or coagulation disorders, will also be excluded. No. 62: To also exclude participants with recurrent infections No. 69: To exclude participants who are unwilling to discontinue all pain medication	To better define the participant population and achieve consistency with the Benefit/Risk Assessment.

Section # and Name	Description of Change	Brief Rationale
Section 7.1 Study stopping criteria	Included links to SAE reporting and to the Safety Management Plan. Removed "the same," so that any 2 related SAEs would trigger the stopping of the study.	To highlight the coordination of S/AE reporting and the conditions of SAE reporting.
Section 7.2 Discontinuation of Study Intervention	Included "clinically significant deterioration of index knee pain."	Clinically significant deterioration of index knee pain warrants discontinuation of study treatment.
Throughout the document	Change "patients" to "participants."	Consistent use of terminology

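### Meeting a Part B stopping criterion in Protocol 7.1 mandates only a recruitment halt; nothing in the Protocol or SAP requires a pause in weekly dosing of the other enrolled participants

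*Protocol*

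**What the plan says.** Protocol 7.1 opens with one instruction covering both parts: "Recruitment will be halted by the sponsor if any of the following occur in participants receiving GSK3858279". For Part B the criteria are two participants with a related SAE, two with the same significant clinical or laboratory abnormality, or two with clinically significant mucocutaneous bleeding. The section then says when recruitment may be resumed: after a positive review by the Principal Investigators, Medical Monitor and SRT, and "following approval to restart the study from the regulatory agencies and ethics committees". Dosing is not mentioned.

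Protocol 6.7 does contain a dosing halt, under Part A: dosing is to be "halted and progression to the next higher dose level stopped if" listed events occur. Its Part B line only sends the reader elsewhere: "Part B: Please see Dose Adjustment Pharmacokinetic Criteria (Section 7.2.3".

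Protocol 4.1.1 gives Part B weekly subcutaneous injections for 8 weeks. The schedule of activities places the doses on Days 1, 8, 15, 22, 29, 36, 43 and 50.

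The amendment history bears on intent only. The Amendment 4 rationale for the SAE criterion is that "any 2 related SAEs would trigger the stopping of the study".

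**The concern.** A recruitment halt is nearly a full stop in Part A, where each person receives one dose. In Part B it is not. Someone who has had k doses when a criterion is met has 8 − k left, so up to seven further injections of 240 mg, and 7.1 does not order any of them held.

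Followed to the letter, the rule protects people who have not yet enrolled. Whether those sharing the exposure that prompted the stop receive next week's injection depends on someone using discretion. Part B is this study's first repeat dosing of an antibody that had not been given to humans before Part A, and drug levels build up with weekly dosing.

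**Working it through.** **What the text requires.** The plan states no figure to reproduce. The check is whether any other Part B provision supplies a mandatory, part-wide dosing pause tied to a 7.1 event.

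| Provision | What it does | Why it does not close the gap |
|---|---|---|
| Protocol 7.2, 7.2.1, 7.2.2 | Withdraws the participant who has a listed event | Affected participant only; mucocutaneous bleeding, a 7.1 trigger, is not listed, and other serious or severe events are left to discretion |
| Protocol 7.2.3 | Pharmacokinetic dose adjustment (body not in the public copy) | Its title and the Amendment 5 log show that it concerns Cmax and AUC limits |
| Protocol 7.2.4 | Investigator may withhold one dose | Optional; affected participant only |
| Protocol 8 | Immediate safety concerns go to the sponsor | Decision about that participant |
| Protocol 10.1.5 | SRT may alter study conduct | Optional; not tied to 7.1 |
| Protocol 10.1.9, 10.1.1 | Sponsor may terminate; urgent hazard changes need no prior ethics approval | Permits action, does not require it |
| SAP 3.1, 2.3 | Two planned safety reviews can decide on dosing | Timed by participants 8 and 20 reaching Week 4, not by a 7.1 event |
| Protocol 2.3.1 | Part B will be halted | COVID-19 outbreak only |

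None of these is at once mandatory, part-wide and triggered by 7.1.

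**How many are affected.** SAP 7.1.5.1 (Interim Analysis 2) expects about 45 randomised when 28 reach Week 8.

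- On treatment: 45 − 28 = 17, about 17/2 = 8.5 on active, if none has discontinued.
- Doses left, r, spread evenly: 1 to 7 if reaching Week 8 means the Day 50 dose has been given; 0 to 7 if it means Week 8 is complete.
- Doses outstanding: 17 × 4.0 = 68, or 17 × 3.5 = 59.5.
- Doses missed in a pause of w weeks = 17 × mean of min(r, w):

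| Pause (weeks) | r = 1 to 7 | r = 0 to 7 |
|---|---|---|
| 1 | 17 × 7/7 = 17.0 | 17 × 7/8 = 14.9 |
| 2 | 17 × 13/7 = 31.6 | 17 × 13/8 = 27.6 |
| 4 | 17 × 22/7 = 53.4 | 17 × 22/8 = 46.8 |
| 7 | 17 × 28/7 = 68.0 | 17 × 28/8 = 59.5 |

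**Cost to the analysis of pausing, if missed doses are not made up.** SAP 14.1.1 drops anyone missing more than 1 of 8 doses from the Per Protocol set: nobody after 1 week; from 2 weeks on, 17 × 6/7 = 14.6 or 17 × 6/8 = 12.8.

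SAP 7.1.4 excludes pain scores from last dose + 7 days in anyone who stops treatment. Missing only the Day 50 dose gives Day 43 + 7 = Day 50, so all of Week 8 (Days 50 to 56) is lost. If none of the 14.9 to 17 with doses left resumes, the Week 8 standard error grows by at most:

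- with 45 participants: √(45/30.1) = 1.22 to √(45/28) = 1.27;
- with the planned 50: √(50/35.1) = 1.19 to √(50/33) = 1.23.

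Earlier weeks inform the repeated measures model, so the true loss is smaller.

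**Exposure, for illustration only.** This assumes the 18-day half-life in SAP 14.6.2, linear one-compartment decline and no absorption lag. Weekly retention is d = 2^(−7/18) = 0.764. In single-dose units, the level just after dose k is (1 − d^k)/(1 − d): 1.76 after dose 2 and 3.39 after dose 6.

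Four weeks after a second dose:

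- dosing continued: 3.39 just after dose 6, 3.39 − 1 = 2.39 just before it;
- dosing paused: 1.76 × d⁴ = 1.76 × 0.340 = 0.60.

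One undosed week leaves 76% of the drug, so a pause prevents build-up rather than clearing drug quickly.

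**The case against.** The strongest reply is that the operating detail sits in documents not available here. Protocol 4.1 has the SRT work to its Charter, with oversight described in the Safety Management Plan, and 10.1.5 places the SRT's actions in the Charter. The Amendment 3 log says that in-stream review under both is meant to ensure adherence to the stopping criteria. This stands: the finding covers the Protocol and SAP only. If a pause exists elsewhere, 7.1 should say so, because 7.1 is where a site will look.

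Second, the title of 7.1 and the approval needed to restart the study already point to a full stop, so continued dosing would be a strained reading. This also stands as evidence of intent. It still leaves a site to infer whether to give the next injection.

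Third, a reader might infer that the recruitment wording is simply left over from a single-dose design. Amendment 2 has "Recruitment will be halted by the sponsor (and may be resumed after appropriate positive review of safety findings" at a time when Part B was one intravenous dose, and Amendment 3's purpose was "To adjust the design of Part B from a single intravenous dose to repeat weekly subcutaneous injections over a period of 8 weeks". The log does not establish this. The Amendment 2 sentence is in the rationale column and may be older. Section 7.1 was then adjusted in Amendment 3 for cohort size and study duration, and again in Amendment 4. Where the wording came from remains inference, and the finding does not need it.

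Fourth, an automatic pause would also follow two matching laboratory abnormalities that only plausibly relate to drug, on investigator judgement, in a blinded part. Graded SRT discretion is a defensible alternative there. That argues for a quick review and a clear route to resumption; it does not justify silence on dosing.

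**Conclusion.** The gap is real in the Protocol and SAP. A Part B criterion in 7.1 mandates a recruitment halt and nothing more, and no other operative sentence requires dosing of the remaining enrolled participants to pause. It should be fixed. Confidence is medium, because the SRT Charter and Safety Management Plan may already cover it.

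A reader might go further and infer that the sponsor chose to keep dosing through a stop. The documents do not support that: the title, the restart approval and the Amendment 4 rationale point the other way.

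The size is about 17 people on treatment at one snapshot, assuming no discontinuations and even spread, with 15 to 17 doses due in the first week of a review. This counts scheduled doses. It does not measure harm, and the likelihood of a trigger has not been estimated. The exposure contrast, about 2.4 (pre-dose) to 3.4 (post-dose) against 0.6 single-dose units, rests on an assumed linear model, whereas the preclinical model in Protocol 4.4.1 is target-mediated. The textual finding does not depend on it.

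**What to change.** In Protocol 7.1, cross-referenced from the Part B line of 6.7, state that when a Part B criterion is met:

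- recruitment and further dosing of enrolled Part B participants are paused;
- dosing of enrolled participants may resume only after a documented positive review by the Principal Investigators, Medical Monitor and SRT, and any approval that the regulators or ethics committees require;
- the existing approval still applies before recruitment restarts;
- safety visits continue during the pause.

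If the SRT Charter or Safety Management Plan already requires this, a pointer from 7.1 that covers all three criteria is enough.

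The drafting cost is small. The trial pays only if a criterion is met: at the snapshot above, about 15 to 17 doses for a 1-week pause, about 13 to 15 people out of the Per Protocol set once it lasts 2 weeks or more, and, if none resumes, at most the 19% to 23% wider Week 8 standard error with 50 participants (22% to 27% with 45). SAP 2.3 allows a larger sample to account for discontinuations, which could offset part of that.
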